On Day 1 and on the first day of re-initiation of study drug when post-dose monitoring is required, significant findings, which in view of the first-dose administrator meet the definition of AE, have an onset after the study drug intake and are resolved at the time of discharge from the cardiac monitoring, must be recorded directly on the Adverse Event page of the separate eCRF by the first-dose administrator / delegate. These AEs will not be visible to any of the blinded study personnel at the study site. During the study, all clinical records related to first-dose data (e.g., 12-lead ECG printouts, BP results, AEs, etc.) must be filed in a separate medical chart only visible to the first-dose administrator.

All other AEs (i.e., those with an onset prior to study drug intake or which are not resolved at the time of discharge from the cardiac monitoring or with an onset after discharge from the cardiac monitoring), as well as all SAEs and all AEs requiring study drug discontinuation must be reported to the principal investigator / treating neurologist, who will record these events on the AE page of the eCRF.

The 3-hour PK sample on Day 1 or on the first day of re-initiation of study drug when post-dose monitoring is required should be taken by the first-dose administrator, the first-dose administrator nurse or another person not involved in the clinical care and management of the study subject.

Any cardiac events of potential clinical concern on Day 1 and on the first day of re-initiation of study drug when post-dose monitoring is required must be assessed by the first-dose administrator for seriousness. In addition, the first-dose administrator should determine the need for medical management and assist the treating neurologist in deciding what actions should be taken on study treatment, if any. In case of such events, the first-dose administrator may consult with a cardiologist. In case of acute cardiac events, and if the first-dose administrator is not adequately trained and experienced in cardiology and is not equipped to provide emergency treatment, she/he will refer the subject to a cardiologist to receive emergency care and treatment.

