At Visit 3 (Day 1) and on the first day of re-initiation of study drug when post-dose monitoring is required, significant findings, which in view of the first-dose administrator meet the definition of a (non-serious) AE, have an onset after the study drug intake, and are resolved at the time of discharge of the subject from cardiac monitoring, must be recorded directly on the AE page of the separate eCRF by the first-dose administrator / delegate. These AEs will not be visible to any of the blinded study personnel at the study site. All other significant findings on Day 1 or on the first day of re-initiation of study drug when post-dose monitoring is required that are serious or unresolved at the time of discharge of the subject from cardiac monitoring or with an onset on any other day, which in her/his view meet the definition of an AE, must be reported to the principal investigator / treating neurologist who will record these events on the AE page of the eCRF.

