At Visit 3 (Day 1) and at visits for re-initiation of study drug when post-dose monitoring is required, the assessment of vital signs will be performed under the responsibility of the first-dose administrator who will also evaluate and interpret these assessments. At all other visits, it will be performed under the responsibility of the treating neurologist or the first-dose administrator, depending on the site setting [see Sections 3.7.2 and 3.7.4].

On Day 1 and on the first day of re-initiation of study drug when post-dose monitoring is required, significant findings, which in view of the first-dose administrator meet the definition of an AE, have an onset after the study drug intake, and are resolved at the time of discharge of the subject, must be recorded directly on the AE page of the separate eCRF by the first-dose administrator / delegate. These AEs will not be visible to any of the blinded study personnel at the study site. All other significant findings on Day 1 or on the first day of re-initiation of study drug when post-dose monitoring is required that are unresolved at the time of discharge of the subject from cardiac monitoring or with an onset on any other day which in her/his view meet the definition of an AEs must be reported to the principal investigator / treating neurologist who will record these events on the AE page of the eCRF.

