10.1.5 Reporting of adverse events

All AEs occurring after study start (i.e., signing of informed consent) and up to 30 days after study treatment discontinuation or up to the last visit of the PTOP (i.e., Week 156 visit of the PTOP) (whichever is latest) must be recorded on specific AE pages of the eCRF. Actelion may contact the investigator to obtain further information.

Cardiac events

The first-dose administrator [see Section 3.7.4] must ensure that blinded study personnel at the study site, such as the treating neurologist, efficacy assessor, clinical coordinator / study nurse, and other personnel involved in the clinical care and management of the subject, do not have access to Day 1 and day of re-initiation of study drug post-dose BP assessments or ECGs interpretation reports, or to AEs with onset after the study drug intake on Day 1 or on the first day of re-initiation of study drug and which are resolved at the time of discharge.

However, significant findings (e.g., new ECG abnormalities, bradycardia) that meet the definition of an AE must be recorded on the AE page of the eCRF.

On Day 1 and on the first day of re-initiation of study drug when post-dose monitoring is required, significant findings that, in view of the first-dose administrator, meet the definition of an AE, have an onset after the study drug intake, and are resolved at the time of discharge of the subject from cardiac monitoring, must be reported directly on the AE page of the separate eCRF by the first-dose administrator / delegate. These AEs will not be visible to any of the blinded study personnel at the study site. All other significant findings on Day 1 and on the first day of re-initiation of study drug when post-dose monitoring is required but unresolved at the time of discharge from cardiac monitoring of the subject, which in her/his view meet the definition of an AE, must be reported to the principal investigator / treating neurologist who will record these events on the AE page of the eCRF. Similarly, any AEs with onset on Day 1 or on the first day of study drug re-initiation when post-dose monitoring is required leading to the premature discontinuation of study drug must be reported by the first-dose administrator to the principal investigator / treating neurologist who will record these events on the AE page of the eCRF.

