10.2.5 Reporting procedures

All SAEs must be reported by the investigator to the Actelion drug safety department within 24 hours of the investigator's first knowledge of the event.

The MS relapses and associated symptoms are exempt from being reported on an SAE form by the investigator to the Actelion drug safety department with the exceptions described in Section [10.1.6](#).

All SAEs must be recorded on an SAE form, irrespective of the study treatment received by the subject, and whether or not this event is considered by the investigator to be related to study treatment.

The SAE forms must be faxed to the Actelion drug safety department (contact details are provided on the SAE form). The investigator must complete the SAE form in English, and must assess the causal relationship of the event to study treatment.

FU information about a previously reported SAE must also be reported within 24 hours of receiving it. The Actelion drug safety department may contact the investigator to obtain further information.

If the subject is hospitalized in a hospital other than the study site, it is the investigator's responsibility to contact this hospital to obtain all SAE relevant information and documentation.

The reference safety document to assess expectedness of a suspect serious adverse reaction and reported by the sponsor to health authorities, IRBs/IECs and investigators, is the reference safety information section of the IB [[Ponesimod IB](#)].

MS relapses and associated symptoms are commonly seen with the underlying disease and are therefore expected to occur in this subject population. The MS relapses and associated symptoms reported as serious (unless fatal) are waived and will be treated as expected and will therefore not require systematic unblinding or expedited reporting to health authorities, IRBs/IECs, and investigators. However, all MS relapses (irrespective of seriousness) will be collected on the specific relapse pages of the eCRF in the clinical trial database and monitored during the study by the sponsor and by the IDMC.

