12 DATA HANDLING

12.1 Data collection

The investigator/delegate is responsible for ensuring the accuracy, completeness, and timeliness of the data reported. All source documents should be completed in a neat, legible manner to ensure accurate interpretation of the data. Data reported in the eCRF derived from source documents must be consistent with the source documents.

Electronic CRF data will be captured via electronic data capture (using the Rave system provided by Medidata Solutions, Inc., a web-based tool). The investigator and site staff will be trained to enter and edit the data via a secure network, with secure access features

(username, password and identification – an electronic password system). A complete electronic audit trail will be maintained. The investigator/delegate will approve the data (i.e., confirm the accuracy of the data recorded) using an electronic signature (refer to 21 CFR Part 11). In addition to the main eCRF, a separate eCRF will be used to collect data with unblinding potential generated on Day 1 and on the first day of re-initiation of study drug when post-dose monitoring is required. This data will only be visible to the site monitor, the first-dose monitor and to an Independent Data Management Team [see Sections 5.1.4.2 and 10.1.5].

Entries recorded by the subject in the electronic diary (FSIQ-RMS, SF-36v2TM, and WPAI:MS) and the eC-SSRS are considered source data. The site staff will review and ensure completeness and readability (if applicable) of the subject's entries.

Subject screening and enrollment data will be completed for all subjects (i.e., eligible and non-eligible) through the IRT system and eCRF.

For each subject enrolled, regardless of study treatment initiation, a eCRF must be completed and signed by the investigator/delegate. This also applies to those subjects who fail to complete the study. If a subject withdraws from the study, the reason must be noted on the eCRF.

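### Section 10.1.5, with 7.3.2, 5.1.4.2 and 8.2.1, omits the serious-event exception stated in 3.7.2, 3.7.4 and 7.3.1, so the instructions for a serious first-dose event that resolves before discharge contradict each other

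*Protocol*

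**What the plan says.** On Day 1, and on any re-initiation day with post-dose monitoring, a first-dose administrator watches the subject so that blinded site staff do not see heart-rate and conduction effects. Adverse events are split between a separate, hidden eCRF and the main eCRF kept by the principal investigator / treating neurologist.

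- **10.1.5** sends to the hidden eCRF findings that meet the AE definition and start after dosing: those that "are resolved at the time of discharge of the subject from cardiac monitoring, must be reported directly on the AE page of the separate eCRF". The investigator receives the other findings, described as those "but unresolved at the time of discharge from cardiac monitoring of the subject, which in her/his view meet the definition of an AE", and also AEs "leading to the premature discontinuation of study drug must be reported by the first-dose administrator to the principal investigator / treating neurologist".
- **7.3.1** (ECG) limits the hidden route to non-serious AEs and passes to the investigator findings "that are serious or unresolved at the time of discharge of the subject from cardiac monitoring".
- **7.3.2** (blood pressure) uses a near-identical paragraph without the seriousness limit and passes on findings "that are unresolved at the time of discharge of the subject from cardiac monitoring".
- **3.7.2** exempts only non-serious first-dose AEs from the treating neurologist's recording duty.
- **3.7.4** has an unqualified hidden-eCRF sentence, but its next paragraph lists AEs with other onset or not resolved, "as well as all SAEs and all AEs requiring study drug discontinuation must be reported to the principal investigator" / treating neurologist.
- **5.1.4.2** and **8.2.1** carry the unqualified hidden-eCRF sentence and say nothing about SAEs there.
- **10.1.5** and **3.7.4** each also require the first-dose administrator to make sure that the treating neurologist and other blinded staff have no access to first-dose AEs resolved at discharge. Neither sentence excepts serious events.

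**The concern.** Section 1.3.2.4 names transient effects on heart rate and AV conduction as the most prominent safety signal of ponesimod. The hidden route exists for exactly these events. The adverse-event reporting section, where site staff would look for the rule, leaves out the exception that three other sections make for serious events.

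Two things are at stake. First, a serious first-dose event could be entered only on the hidden eCRF, so that its SAE report is late or missing. Second, sites that follow different sections would handle the same event differently, and the main-eCRF record of first-dose serious events would then depend on which section was read.

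**Working it through.** The protocol gives no figure to reproduce, so the check sets the passages side by side.

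| Section | Hidden eCRF limited to non-serious AEs? | Passed to the investigator |
|---|---|---|
| 3.7.2 | Yes | Serious ones, by implication |
| 3.7.4, routing | Not in the sentence itself | Other onset, unresolved, all SAEs, AEs requiring discontinuation |
| 3.7.4, no-access | No limit on what is withheld | – |
| 5.1.4.2 | No | Not stated |
| 7.3.1 | Yes | Serious, unresolved, or onset on another day |
| 7.3.2 | No | Unresolved, or onset on another day |
| 8.2.1 | No | Not stated |
| 10.1.5, routing | No | Unresolved, or leading to discontinuation |
| 10.1.5, no-access | No limit on what is withheld | – |

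**Test case.** Take an event that is serious, starts after dosing, resolves before discharge and does not stop the drug.

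1. Under 3.7.2, 7.3.1 and the routing paragraph of 3.7.4, it goes to the investigator.
2. Under 10.1.5 and 7.3.2, it meets every test for the hidden eCRF and none for the investigator. Under 5.1.4.2 and 8.2.1, it also meets the hidden-eCRF tests.
3. Under the no-access sentences of 10.1.5 and 3.7.4, the first-dose administrator must keep it from the treating neurologist. Section 3.7.4 therefore contradicts itself.
4. Section 10.1.5 keeps one half of the 3.7.4 exception (events leading to discontinuation) and drops the other (SAEs). That looks like an omission, not a deliberate choice.

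**Can the case occur?** Section 1.3.2.4 says that the heart-rate changes, occasionally with second-degree AV block, resolve largely within 6–10 hours. Under 5.1.10, monitoring lasts 4 to 12 hours and discharge requires that no significant ECG abnormality persists. Resolution before discharge is therefore the usual course. Section 5.1.12.1 requires discontinuation for HR < 30 bpm, for symptomatic HR < 40 bpm sustained for at least 1 hour, for QTcF > 500 ms, and for failing the discharge criteria at 12 hours. A resolved AV block is not itself on that list, so the discontinuation route need not catch one judged medically significant.

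**Do the SAE rules close the gap?** Section 10.2.2 requires all SAEs on AE pages and SAE forms. Section 10.2.5 adds: "All SAEs must be reported by the investigator to the Actelion drug safety department" within 24 hours of the investigator's first knowledge. Neither has a first-dose exception, so the duty to report stands. The duty runs through the investigator's knowledge, however, and the hidden eCRF does not supply it. On the separate eCRF, 12.1 says: "This data will only be visible to the site monitor, the first-dose monitor and to an Independent Data Management Team". Section 5.1.4.2 bars both monitors from passing potentially unblinding information to the rest of the site team or the sponsor study team. Section 10.1.3 also requires causality to be judged by an investigator who is a qualified physician, while 3.7.4 allows a non-physician as first-dose administrator.

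**Size.** The instruction applies to about 600 Day 1 visits and to every monitored re-initiation. The protocol gives no first-dose SAE rate. Assuming 0.1% to 0.5% in the ponesimod arm, 300 × 0.001 = 0.3 and 300 × 0.005 = 1.5 events on Day 1. Only those that resolve before discharge and do not stop the drug fall in the gap.

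**The case against.** The strongest reply is that the protocol, read as a whole, does not let a serious event escape. SAEs have their own section, 10.2, and the hidden eCRF is not the SAE channel. The cardiac paragraph of 10.1.5 refers to 3.7.4, which tells the same person to report all SAEs to the investigator, to assess cardiac events of potential clinical concern for seriousness, and to help the treating neurologist decide on study treatment. Section 5.1.4.2 lets the two talk where subject safety requires it, and it gives the sponsor's first-dose monitor medical review of the ECG and blood-pressure data. Section 10.1.5 itself passes on AEs that lead to discontinuation, which covers much of the serious cardiac range.

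Most of this stands. A reader might infer that the protocol sends every resolved first-dose event round the investigator and the 24-hour SAE route, or that the treating neurologist would necessarily be left unaware. The documents do not support either reading: 3.7.4, 10.2.2 and 10.2.5 require the report, and 3.7.4 and 5.1.4.2 keep a line open to the neurologist. It would also be wrong to say that 3.7.4 confines its hidden-eCRF sentence to non-serious events; it reaches that result through the separate SAE sentence.

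What the reply does not remove is the contradiction. The section that 10.1.5 points to also contains a no-access instruction without an exception for serious events, so following the cross-reference brings the first-dose administrator to both the order to disclose and the order to withhold.

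**Conclusion.** The point holds as an internal inconsistency in safety reporting. For a serious first-dose event that resolves before discharge and does not lead to discontinuation, 10.1.5 and 7.3.2 give one route and 3.7.2, 3.7.4 and 7.3.1 another. Sections 5.1.4.2 and 8.2.1 repeat the unqualified hidden-eCRF sentence, though not the rule on what goes to the investigator. The no-access sentences in 10.1.5 and 3.7.4 conflict directly with the SAE rule in 3.7.4.

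A late or missed SAE report is a risk if 10.1.5, 5.1.4.2, 7.3.2 or 8.2.1 is followed alone. It is not what the protocol as a whole prescribes. Expected numbers are small (0.3 to 1.5 Day 1 events on the ponesimod arm before the further restrictions, on an assumed rate that the protocol does not give). No efficacy analysis is affected. The correction is still worth making, because it concerns serious events in the drug's leading known risk area and costs almost nothing.

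**What to change.** Reconcile all the passages to the rule already written in 7.3.1:

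1. Limit the separate-eCRF sentences in 10.1.5, 3.7.4, 5.1.4.2, 7.3.2 and 8.2.1 to non-serious AEs.
2. In 10.1.5 and 7.3.2, widen the class of findings passed to the principal investigator / treating neurologist from unresolved to serious or unresolved.
3. Add the same non-serious limit to the two no-access sentences in 10.1.5 and 3.7.4. Without this step the contradiction survives the other edits.

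The cost is wording in five sections. The treating neurologist may learn of a rare serious first-dose event, which 3.7.4 and 7.3.1 already accept. The efficacy assessor stays masked under 3.7.3 and 5.1.4.2. Dosing, monitoring and the statistical analyses do not change.

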10.1.6 Reporting of MS relapse

All MS relapses during the study must be reported on specific relapse pages of the eCRF.

MS relapses and associated symptoms are not to be entered on the AE page of the eCRF with the following exceptions:

- MS relapses with fatal outcome (these must always be recorded as an AE on the AE page in addition to being reported as SAEs).
- MS relapses that, in the view of the investigator, warrant specific notice due to unusual frequency, severity or remarkable clinical manifestations (these should be reported as an AE on the AE page of the eCRF and, if applicable, on the SAE form).

10.1.7 Follow-up of adverse events

AEs still ongoing more than 30 days after study treatment discontinuation must be followed up until they are no longer considered clinically relevant, or until the event outcome is provided.

10.2 Serious adverse events

10.2.1 Definitions of serious adverse events

10.2.1.1 Serious adverse events

An SAE is defined by the ICH guidelines as any AE fulfilling at least one of the following criteria:

- Fatal.
- Life-threatening: refers to an event in which the subject was at risk of death at the time of the event. It does not refer to an event that hypothetically might have caused death had it been more severe.
- Requiring inpatient hospitalization or prolongation of existing hospitalization.
- Resulting in persistent or significant disability or incapacity.
- Congenital anomaly or birth defect.
- Medically significant: refers to important medical events that may not immediately result in death, be life-threatening, or require hospitalization but may be considered to be SAEs when, based upon appropriate medical judgment, they may jeopardize the subject and may require medical or surgical intervention to prevent one of the outcomes listed in the definitions above.

The following reasons for hospitalization are exempted from being reported:

- Hospitalization for cosmetic elective surgery, or social and/or convenience reasons.
- Hospitalization for MS relapse (with the exceptions described in Section 10.1.6).
- Hospitalization for pre-planned (i.e., planned prior to signing informed consent) surgery or standard monitoring of a pre-existing disease or medical condition that did not worsen, e.g., hospitalization for coronary angiography in a subject with stable angina pectoris.

However, complications that occur during hospitalization are AEs or SAEs (e.g., if a complication prolongs hospitalization).

10.2.1.2 Serious adverse events associated with the study design or protocol-mandated procedures

An SAE is defined as related to study design or protocol-mandated procedures if it appears to have a reasonable possibility of a causal relationship to either the study design or to protocol-mandated procedures. Examples include discontinuation of a subject's previous treatment during a washout period leading to exacerbation of underlying disease or a complication of an invasive procedure that is specifically required by the protocol.

10.2.2 Reporting of serious adverse events

All SAEs occurring after study start (i.e., signing of informed consent) up to 30 days after study treatment discontinuation must be reported on AE pages in the eCRF and on SAE forms, regardless of the investigator-attributed causal relationship with study treatment or study-mandated procedures.

